10. MEASUREMENT OF EFFECT

Although response is not the primary endpoint of this trial, participants with measurable and/or non-measurable disease will be assessed by RECIST 1.1 criteria. For the purposes of this study, participants should be reevaluated every 8 weeks. In addition to a baseline scan, confirmatory scans and clinical measurements with calipers (if applicable) should also be obtained ≥ 4 weeks following initial documentation of an objective response.

10.1 Antitumor Effect– Solid Tumors

For the purposes of this study, participants should be re-evaluated for response every 8 weeks. Confirmatory scans should be obtained not less than 4 weeks following initial documentation of objective response.

Response and progression will be evaluated in this study using the new international criteria proposed by the Response Evaluation Criteria in Solid Tumors (RECIST) (Eisenhauer et al., 2009) guidelines. Changes in the diameter (unidimensional measurement) of the tumor lesions are used in the RECIST criteria.

10.1.1 Definitions

Evaluable for PFS. All participants randomized on this study are considered to be evaluable for PFS (whether or not they are eligible, have measurable disease, or receive protocol therapy).

Evaluable for toxicity. All participants who receive at least one dose of study treatment will be evaluable for toxicity from the time of their first treatment.

CONFIDENTIAL

This document is confidential. Do not disclose or use except as authorized.

Evaluable for objective response. Only those participants who have measurable disease present at baseline and have had their disease re-evaluated will be considered evaluable for response. These participants will have their response classified according to the definitions stated below. (Note: Participants who exhibit objective disease progression or die prior to the end of cycle 1 will also be considered evaluable.)

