14.4 Analysis of Secondary Clinical Endpoints

Safety and toxicity: All patients who received at least one dose of protocol therapy (fulvestrant, ganetespib, or both) will be included in the safety/toxicity analysis. Toxicity will be graded according to NCI CTCAE, Version 4.0. The proportion of patients who experience each type and grade of toxicity will be presented in tabular form. Toxicity will be described separately in Arm A (pre-crossover), Arm C (post-crossover), and Arm B.

Objective Response Rate: All patients with measurable disease at baseline will be included in the analysis of response rate. Response will be assessed using RECIST 1.1, as described in Section 10. The response rate will be calculated separately in Arms A, B, and C. Response rates in Arm A and Arm B will be compared using a one-sided Fisher exact test. An intent to treat analysis will be used, so all patients randomized in the measurable disease stratum will be used in the

analysis; patients with no follow-up response evaluation will be assumed to be non-responders. Assuming that 57 patients are entered in the measurable disease stratum, there will be 81% power to decide that the ganetespib arm has a better response rate if the true response rates on the two arms are as different as 36% and 5%, or 44% and 10%.

Clinical benefit rate: Clinical benefit will be defined as CR + PR + SD \geq 6 months. All patients will be included in the analysis of clinical benefit. CBR will be calculated separately in Arms A and B, and compared using a one-sided Fisher exact test. All patients randomized on study will be used in this analysis, and patients with no follow-up response evaluation will be assumed not to have clinical benefit. With 71 patients randomized, there will be 80% power to decide that the ganetespib arm has a better clinical benefit rate if the true benefit rates on the two arms are as different as 63% and 30%, or 73% and 40%.

Overall survival: Overall survival is defined as duration of time from randomization to death due to any cause, or censored on the date last known alive. All randomized patients will be included in the analysis of OS. OS will be estimated separately in Arm A and Arm B. OS will be analyzed at the same time as the final analysis of PFS, although it is acknowledged that the percent of survival censoring at that time will be larger than the percent of PFS censoring, and this will limit the power to detect survival differences between the arms.

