14.6 Reporting and Exclusions

14.6.1 Evaluation of toxicity.

All participants will be evaluable for toxicity if they received any protocol therapy.

14.6.2 Evaluation of response.

All participants randomized on the study who have RECIST measurable disease must be assessed for response to treatment, even if there are major protocol treatment deviations, or they receive no treatment, or if they are ineligible. Participants who have no follow-up tumor evaluations, who die or receive non-protocol anticancer therapy before a response is noted, or who have unknown or not-assessable response will count as non-responders.

CONFIDENTIAL

This document is confidential. Do not disclose or use except as authorized.

14.6.3 Evaluation of progression-free survival.

All participants randomized on the study must be assessed for PFS, even if there are major protocol treatment deviations, or they receive no treatment, or if they are ineligible. However, there will be no imputation of any missing progression-free survival times.

14.6.4 Analyses of Subsets of Patients.

For all endpoints except toxicity, the primary analysis will be based on all randomized patients (and the primary analysis of toxicity will be based on all patients who receive at least one dose of one of the study agents). However, in addition to the primary analysis, analysis of subsets of patients may be done (e.g., analysis restricted to eligible patients or to patients who receive at least one cycle of therapy). However, these analyses of subsets will be considered exploratory and will not serve as the basis for drawing conclusions about treatment efficacy.

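### Section 10.1.1 limits the response population to re-evaluated patients, which contradicts the intention-to-treat response analysis in Sections 14.4 and 14.6.2 (minor, secondary endpoint)

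*Combined protocol and SAP*

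**What the plan says.** Section 10.1.1 (Definitions) defines who is evaluable for each outcome. Its entry on response reads: "Only those participants who have measurable disease present at baseline and have had their disease re-evaluated will be considered evaluable for response". A note adds one exception: "Participants who exhibit objective disease progression or die prior to the end of cycle 1 will also be considered evaluable".

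Section 14.4 (Analysis of Secondary Clinical Endpoints) sets a wider population: "All patients with measurable disease at baseline will be included in the analysis of response rate". It applies the intention-to-treat principle within the measurable-disease stratum and adds that "patients with no follow-up response evaluation will be assumed to be non-responders".

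Section 14.6.2 (Evaluation of response) agrees with Section 14.4. It opens with "All participants randomized on the study who have RECIST measurable disease must be assessed for response to treatment" and extends this to untreated and ineligible patients. Its list of non-responders begins with "Participants who have no follow-up tumor evaluations, who die or receive non-protocol anticancer therapy before a response is noted". The same list takes in patients whose response is not known or could not be assessed.

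Section 14.6.4 makes all randomized patients the primary set for every endpoint except toxicity and calls subset analyses exploratory. The response objective in Section 1.3 requires measurable disease at baseline and nothing more.

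**The concern.** A patient with measurable disease who never has a follow-up scan is outside the response population under Section 10.1.1, but is a non-responder under Section 14. Such a patient is either left out of the denominator or counted in it as a failure.

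The narrower text is easily read as an analysis set. Section 10.1.1 has three parallel entries. Those for progression-free survival (all randomized) and toxicity (at least one dose) match the Section 14 analysis sets, and only the response entry does not. Section 14.4 also refers the reader to Section 10 for how response is assessed.

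At stake is the denominator of a secondary endpoint. Leaving out patients without a scan can only raise the rate, because none of them can be a documented responder. With two rules in the text, the choice between them could be made after the data are seen.

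**Working it through.** **Inputs.** Total 71 patients, at most 14 with non-measurable disease, 1:2 allocation (Section 14.2). For response: 57 measurable patients, one-sided Fisher exact test, 81% power for 36% v 5% or 44% v 10% (Section 14.4). The significance level for the response test is not stated. One-sided 0.05 is assumed, as for the primary log-rank test.

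**1. Reproduce the stated power.** 71 - 14 = 57, which splits 1:2 into 19 (Arm A) and 38 (Arm B). Exact power, by enumerating both binomials:
- 36% v 5%: 80.8%
- 44% v 10%: 81.0%

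Both round to the stated 81%. One-sided 0.025 gives about 73% and 71%, and a pooled normal approximation gives about 88%, so neither fits. The stated figure therefore uses all 57 measurable patients, which is the Section 14 population, with no deduction for patients not re-evaluated.

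**2. Effect of the Section 10.1.1 denominator on the rate.** Let d be the share of measurable patients who are neither re-evaluated nor covered by the early progression or death exception. The responders are the same under both rules, so

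rate (10.1.1) = rate (intention to treat) / (1 - d).

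The documents give no d for response, so the values below are assumptions. The 15% matches only the loss allowance that Section 14.2 makes for progression-free survival.

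| d | 36% becomes | 5% becomes |
|---|---|---|
| 5% | 37.9% | 5.3% |
| 10% | 40.0% | 5.6% |
| 15% | 42.4% | 5.9% |
| 20% | 45.0% | 6.3% |

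With the same d in both arms, the ratio of the rates is unchanged, but the difference widens by the same factor. At d = 15% it goes from 31 points to 31/0.85 = 36.5 points.

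**3. Effect on the test.** Take 10 responders of 38 in Arm B and 1 of 19 in Arm A: one-sided Fisher p = 0.055. If 4 of the 38 were not re-evaluated and none of the 19, Section 10.1.1 gives 10/34 v 1/19 and p = 0.036. With 2 of the 38 not re-evaluated, 10/36 v 1/19 gives p = 0.045. These are chosen borderline cases. They show that the denominator can decide the result, not that it is likely to.

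**4. Power under Section 10.1.1.** At d = 15%, 57 x 0.85 is about 48, or 16 v 32.
- Rates held at 36% v 5% or 44% v 10%: 72.0% or 72.6%.
- Rates raised as in step 2, to 42.4% v 5.9% or 51.8% v 11.8%: 83% in both cases.

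The second version is consistent with step 2, because the smaller denominator contains the same responders.

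**The case against.** The strongest reply is that the plan already settles the matter. Sections 14.4 and 14.6.2 each state the intention-to-treat rule, and Section 14.6.4 makes it primary and any subset exploratory. No analysis section calls for a rate on the Section 10.1.1 set. Section 10.1.1 sits in the chapter on measurement, and it can be read as saying whose response can be classified, since a patient without a scan cannot be assigned a category. Much of this stands: Section 14 taken alone yields a single primary response rate, so a reader who infers that the plan prespecifies two goes too far. What it does not remove is an exclusive rule in the current text, placed beside two entries that do define analysis sets, with no statement that Section 14 prevails.

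A second reply concerns who falls in the gap. A reader might infer that patients who stop ganetespib early for toxicity drop out of the denominator. Sections 5, 5.1.15 and 5.7 and Study Calendar D keep such patients on study with imaging about every 8 weeks, so stopping treatment does not by itself mean no scan. This reply stands. The gap is mainly withdrawal, new therapy or loss to follow-up before the first scan, and death after cycle 1 but before that scan.

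A third reply is that unequal loss between arms is not supported. The only loss assumption, in Section 14.2 for progression-free survival, is up to 15% and equal in the two arms. This also stands.

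**Conclusion.** The contradiction is real, but it is a minor matter for a secondary endpoint. If Section 10.1.1 were used as the denominator, the response rate would be inflated by 1/(1-d), from 36% to between 37.9% and 42.4% for an assumed d of 5% to 15%, and a borderline comparison could cross the 0.05 level. If every measurable patient is re-evaluated or meets the early exception, the two rules give the same rate.

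Two stronger conclusions are tempting, and the documents do not support them:

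- **That the stated power is wrong.** The 81% reproduces on 19 v 38 and needs no change. The fall to 72% appears only if the rates are held fixed while the denominator shrinks. With the same responders, power is 83%.
- **That the test would exceed its nominal error rate.** Simulation with equal 20% intention-to-treat rates, and an assumed 20% v 5% not re-evaluated in Arms B and A, gives a rejection rate of about 2% under Section 14 and about 4.4% under Section 10.1.1. Both are below 5%, and the unequal loss is hypothetical.

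The primary analysis is unaffected, because Section 10.1.1 itself makes every randomized patient evaluable for progression-free survival. The conclusion rests on the assumed one-sided 0.05 level and on assumed values of d.

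**What to change.** In Section 10.1.1:

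- Delete the condition that disease must have been re-evaluated.
- State that all patients randomized with measurable disease are in the response-rate denominator, and that those with no post-baseline assessment count as non-responders, with a reference to Sections 14.4 and 14.6.2.
- State that any response rate restricted to re-evaluated patients is exploratory, in line with Section 14.6.4.

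The note on progression or death before the end of cycle 1 is then no longer needed to define the denominator.

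The cost is one wording change. The sample size, the stated power and the primary analysis stay as they are. The reported response rate may be slightly lower than an evaluable-only figure.

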10.1.2 Disease Parameters

Measurable disease. Measurable disease is the presence of at least one (1) lesion that can be accurately measured in at least one dimension with longest diameter ≥ 20 millimeters (mm) using conventional techniques (CT, MRI, x-ray) or ≥ 10 mm with spiral CT scan. Measurable lesions must be at least 2 times the slice thickness in mm. All tumor measurements must be recorded in millimeters (or decimal fractions of centimeters).

Malignant lymph nodes. To be considered pathologically enlarged and measurable, a lymph node must be ≥ 15 mm in short axis when assessed by CT scan (CT scan slice thickness recommended to be no greater than 5 mm). At baseline and in follow-up, only the short axis will be measured and followed.

A lesion in a previously irradiated area is not eligible for measurable disease unless there is objective evidence of progression of the lesion prior to study enrollment. Lesions in previously irradiated areas must be clearly identified as such.

Non-measurable disease. All other lesions (or sites of disease), including small lesions (longest diameter < 10 mm or pathological lymph nodes with ≥ 10 to < 15 mm short axis, are considered non-measurable disease. Bone lesions, leptomeningeal disease, ascites, pleural/pericardial effusions, lymphangitis cutis/pulmonis, inflammatory breast disease, abdominal masses identified by physical exam that are not measurable by reproducible imaging techniques, and cystic lesions are all considered non-measurable.

Target lesions. All measurable lesions up to a maximum of 2 lesions per organ and 5 lesions in total, representative of all involved organs, should be identified as target lesions and recorded and measured at baseline. Lesions must be accurately measured in 1 dimension with a minimum size of 10 mm by CT or MRI (slice thickness no greater than 5 mm), 20 mm by *chest* x-ray. Nodes must have a short axis ≥ 15 mm. The short axis of target nodes should be included in the sum of the longest dimension of target lesions in the calculation of response. Nodes that shrink to < 10 mm are considered normal. (If the patient has a sum of largest diameters of target lesions other than nodes that is zero, then the patient can be classified as having a CR if each target node has a short axis < 10 mm). Target lesions should be selected on the basis of their size, be representative of all the involved organs, and should be lesions that can be followed with reproducible repeated measurements.

CONFIDENTIAL

This document is confidential. Do not disclose or use except as authorized.

Lytic bone lesions or mixed lytic-blastic lesions, *with identifiable soft tissue components*, that can be evaluated by cross sectional imaging techniques such as CT or MRI can be considered target lesions if the *soft tissue component* meets the definition of measurability as defined above. Cystic lesions thought to represent cystic metastases can be considered as target lesions. However, if non-cystic lesions are present, these are preferred for selection as target lesions. Lesions in previously irradiated areas or areas subject to other loco-regional therapy are usually not considered measurable unless there has been demonstrated progression of that lesion.

Non-target lesions. All other lesions, including small lesions < 10 mm or pathological lymph nodes measuring ≥ 10 mm to < 15 mm in short axis, as well as truly non-measurable lesions, which include leptomeningeal disease, ascites, pleural or pericardial effusion, inflammatory breast disease, lymphangitic involvement of skin or lung, abdominal masses identified by physical exam that are not measurable by reproducible imaging techniques.

10.1.3 Methods for Evaluation of Measurable Disease

All measurements should be taken and recorded in metric notation, using a ruler, calipers, or digital measurement tool. All baseline evaluations should be performed as closely as possible to the beginning of treatment and never more than 4 weeks before the beginning of the treatment.

The same method of assessment and the same technique should be used to characterize each identified and reported lesion at baseline and during follow-up. Imaging-based evaluation is preferred to evaluation by clinical examination when both methods have been used to assess the anti-tumor effect of a treatment.

Clinical lesions. Clinical lesions will only be considered measurable when they are superficial (e.g., skin nodules and palpable lymph nodes). For the case of skin lesions, documentation by color photography, including a ruler to estimate the size of the lesion, is recommended.

Chest x-ray. Lesions on chest x-ray are acceptable as measurable lesions when they are clearly defined and surrounded by aerated lung; however, CT is preferable.

Conventional CT and MRI. These techniques should be performed with cuts of 10 mm or less in slice thickness contiguously. Spiral CT should be performed using a 5 mm contiguous reconstruction algorithm. This applies to tumors of the chest, abdomen, and pelvis. Head and neck tumors and those of extremities usually require specific protocols.

Ultrasound (US). When the primary endpoint of the study is objective response evaluation, US should not be used to measure tumor lesions. It is, however, a possible alternative to clinical measurements of superficial palpable lymph nodes, subcutaneous

lesions, and thyroid nodules. US might also be useful to confirm the complete disappearance of superficial lesions usually assessed by clinical examination.

FDG PET and PET/CT. The acquisition of FDG PET and FDG PET/CT scans should follow the NCI Guidelines for using FDG PET as an indicator of therapeutic response (L.K. Shankar, J.M. Hoffman, S. Bacharach, M.M. Graham, J. Karp, A.A. Lammertsma, S. Larson, D.A. Mankoff, B.A. Siegel, A. Van den Abbeele, J. Yap, D. Sullivan. Consensus recommendations for the use of 18F-FDG PET as an indicator of therapeutic response in patients in National Cancer Institute Trials. J Nucl Med, 47(6):901-903, 2006). Patients should avoid strenuous exercise and be on a low carbohydrate diet for 24 hours prior to the scan. Patients should fast for 4 hours or longer prior to the FDG injection and should have a serum glucose of less than 200 mg/dL at the time of FDG injection. A 10-20 mCi dose of FDG should be injected for typical adult patients. For longitudinal studies with multiple scans, particular attention should be paid to ensure consistent patient preparation and acquisition parameters between the follow-up scan and the baseline scan. When designing a study where PET scans are going to be utilized as one of the modalities to evaluate efficacy, it is important to consult with physicians in nuclear medicine in designing the appropriate criteria to be utilized.

Note: In this protocol, PET scans are not to be used for primary assessment of response. PET scans and/or PET-CT scans may be used to supplement CT or MRI scans when a clinical question as to response status still exists.

Endoscopy, Laparoscopy. The utilization of these techniques for objective tumor evaluation has not yet been fully and widely validated. Their uses in this specific context require sophisticated equipment and a high level of expertise that may only be available in some centers. Therefore, the utilization of such techniques for objective tumor response should be restricted to validation purposes in reference centers. However, such techniques may be useful to confirm complete pathological response when biopsies are obtained.

Tumor markers. Tumor markers alone cannot be used to assess response. If markers are initially above the upper normal limit, they must normalize for a subject to be considered in complete clinical response. Specific additional criteria for standardized usage of prostate-specific antigen (PSA) and CA-125 response in support of clinical trials are being developed.

Cytology, Histology. These techniques can be used to differentiate between partial responses (PR) and complete responses (CR) in rare cases (e.g., residual lesions in tumor types, such as germ cell tumors, where known residual benign tumors can remain).

The cytological confirmation of the neoplastic origin of any effusion that appears or worsens during treatment when the measurable tumor has met criteria for response or

CONFIDENTIAL

This document is confidential. Do not disclose or use except as authorized.

stable disease is mandatory to differentiate between response or stable disease (an effusion may be a side effect of the treatment) and progressive disease.

10.1.4 Evaluation of Target Lesions

Complete Response (CR): Disappearance of all target lesions. Any pathological lymph node must have reduction in short axis to < 10 mm.

Partial Response (PR): At least a 30% decrease in the sum of the diameters of target lesions, taking as reference the baseline sum diameters.

Progressive Disease (PD): At least a 20% increase in the sum of the diameters of target lesions, taking as reference the smallest sum on study with at least a 5 mm absolute increase in the sum of all lesions. The appearance of one or more new lesions* denotes disease progression.

Stable Disease (SD): Neither sufficient shrinkage to qualify for PR nor sufficient increase to qualify for PD, taking as reference the smallest sum diameters while on study.

Unknown (UN): Assessment of target lesions cannot be made due to insufficient or unevaluable data. In this case, a concise explanation must be given.

Note: If tumor response data is missing for target lesions, the overall assessment must be UN unless there is new disease that would result in an overall assessment of PD. However, if there is missing or unevaluable data for non-target lesions, but data is available for all target lesions, the overall response for that time point will be assigned based on the sum LD of all target lesions. Additionally, the assessment of CR cannot be made if there is missing or unevaluable data for non-target lesions. In this case, the overall assessment would be PR.

***Definition of New Lesion:** The finding of a new lesion should be unequivocal (i.e. not due to difference in scanning technique, imaging modality, or findings thought to represent something other than tumor (ex: new bone lesions may be healing or flare of pre-existing lesions). However, a lesion identified on a follow-up scan in an anatomical location that was not scanned at baseline is considered new and will indicate PD. If a new lesion is equivocal (because of small size, etc.), follow-up evaluation will clarify if it truly represents new disease and if PD is confirmed, progression should be declared using the date of the initial scan on which the lesion was discovered.

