10.1.5 Evaluation of Non-Target Lesions

Complete Response (CR): Disappearance of all non-target lesions and normalization of tumor marker level. All lymph nodes must be non-pathological in size (< 10 mm short axis).

Note: If tumor markers are initially above the upper normal limit, they must normalize for a subject to be considered in complete clinical response.

Incomplete Response/Stable Disease (SD): Persistence of one or more non-target lesions and/or maintenance of tumor marker level above the normal limits.

Progressive Disease (PD): Appearance of one or more new lesions* (new lesions must be > slice thickness) and/or unequivocal progression of existing non-target lesions. Overall level of substantial worsening that merits discontinuation of therapy. A useful test that can be applied when assessing non-targets for unequivocal progression is to consider if the increase in overall disease burden based on the change in non-measurable disease is comparable in magnitude to the increase that would be required to declare PD for measurable disease.

Unknown (UN): Assessment of non-target lesions cannot be made due to insufficient or unevaluable data. In this case, a concise explanation must be given.

***Definition of New Lesion:** The finding of a new lesion should be unequivocal (i.e. not due to difference in scanning technique, imaging modality, or findings thought to represent something other than tumor (ex: new bone lesions may be healing or flare of pre-existing lesions). However, a lesion identified on a follow-up scan in an anatomical location that was not scanned at baseline is considered new and will indicate PD. If a new lesion is equivocal (because of small size, etc.), follow-up evaluation will clarify if it truly represents new disease and if PD is confirmed, progression should be declared using the date of the initial scan on which the lesion was discovered.

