10.1.6 Evaluation of Best Overall Response

The best overall response is the best response recorded from the start of the treatment until disease progression/recurrence (taking as reference for progressive disease the smallest measurements recorded since the treatment started). The participant's best response assignment will depend on the achievement of both measurement and confirmation criteria.

For Patients with Measurable Disease (i.e., Target Disease)

Target Lesions	Non-Target Lesions	New Lesions	Overall Response	Best Overall Response for when Confirmation is Required:
CR	CR	No	CR	≥4 wks confirmation
CR	Non-CR/Non-PD	No	PR	≥4 wks confirmation
CR	Not evaluated	No	PR	
PR	Non-CR/Non-PD/Not evaluated	No	PR	

CONFIDENTIAL

This document is confidential. Do not disclose or use except as authorized.

SD	Non-CR/Non-PD/Not evaluated	No	SD	Documented at least once \geq 4 wks from baseline
PD	Any	Yes or No	PD	No prior SD, PR or CR
Any	PD*	Yes or No	PD	
Any	Any	Yes	PD	
* In exceptional circumstances, unequivocal progression in non-target lesions may be accepted as disease progression.				
Note: Participants with a global deterioration of health status requiring discontinuation of treatment without objective evidence of disease progression at that time should be reported as " symptomatic deterioration ". Every effort should be made to document the objective progression even after discontinuation of treatment.				

For Patients with Non-Measurable Disease (i.e., Non-Target Disease)

Non-Target Lesions	New Lesions	Overall Response
CR	No	CR
Non-CR/non-PD	No	NonCR/non-PD
Not all evaluated	No	Not evaluated
Unequivocal PD	Yes or No	PD
Any	Yes	PD
Non-CR/non-PD is preferred over stable disease for non-target disease since SD is increasingly used an endpoint for assessment of efficacy in some trials so to assign this category when no lesions can be measured is not advised.		

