10.1.8 Progression-Free Survival

Progression-free survival (PFS) is defined as the duration of time from start of treatment until time of progression or death, whichever comes first. Patients who stop protocol-therapy (either ganetespib or fulvestrant or both) for a reason other than progression or death should be followed for progression, as detailed in Study Calendar D until the patient progresses, initiates alternative anti-cancer treatment, dies, or withdraws consent, whichever comes first. If the initiation of non-protocol anti-cancer treatment occurs first, then the patient's PFS will be censored at the time of last disease evaluation before start of the non-protocol anti-cancer treatment.

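### The missing-data note in Section 10.1.4 makes a scan Unknown in cases where Sections 10.1.4 to 10.1.6 otherwise establish progression, and nothing says which rule governs PFS

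*Combined protocol and SAP*

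**What the plan says.** All references are to the combined protocol and SAP.

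- **10.1.4, PD definition.** Target progression is "At least a 20% increase in the sum of the diameters of target lesions" over the smallest sum on study, with at least 5 mm absolute increase. A new lesion also denotes progression.
- **10.1.4, UN definition.** "Assessment of target lesions cannot be made due to insufficient or unevaluable data".
- **10.1.4, note, first sentence.** "If tumor response data is missing for target lesions, the overall assessment must be UN unless there is new disease" that would make the overall assessment PD. No other exception is given.
- **10.1.4, note, second sentence.** This covers missing non-target data where "data is available for all target lesions", and assigns the response from the target sum.
- **10.1.5.** Non-target PD is a new lesion "and/or unequivocal progression of existing non-target lesions".
- **10.1.6, measurable-disease table.** Target Any, non-target PD, new lesions Yes or No gives overall PD. A footnote to non-target PD says that such progression may be accepted exceptionally.
- **10.1.8 and 14.2.** A PFS event is progression or death. If non-protocol therapy starts first, PFS "will be censored at the time of last disease evaluation before start of the non-protocol anti-cancer treatment".
- **5.1.12, 5.1.13 and 10.1.10.** Progression must be confirmed by central review and by the overall investigator before crossover, or before protocol treatment stops for progression.

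**The concern.** The note decides the overall assessment, not only the target-lesion category, and its wording is mandatory. It therefore overrides findings that the neighbouring sections treat as sufficient for progression. Two written rules then classify the same scan differently, and the PFS sections (10.1.8, 14.2, 14.6.3) neither rank them nor say how a UN scan enters the analysis.

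The date, and sometimes the existence, of a primary-endpoint event is at stake. Section 10.1.4 dates an equivocal new lesion back to the scan where it was first seen, once it is confirmed. It has no such provision for a UN scan on which progression was already unequivocal. A scan classified UN also cannot support the central confirmation of progression. The documents describe no blinding or placebo, so a choice between two rules could be made with the arm known.

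**Working it through.** **1. The plan's own figure.** Inputs from 14.2: 57 expected events, medians 4.0 and 8.0 months (hazard ratio 0.5), effective sample 20 v 40 (p = 1/3), one-sided 0.05.

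- Power = Φ(√(d·p·(1−p))·|ln HR| − 1.645) = Φ(√(57 × 2/9) × 0.693 − 1.645) = Φ(2.467 − 1.645) = 0.794. The stated 80% is reproduced.
- Expected events with 20 months of accrual and 20 of follow-up, under exponential PFS, are 56.5 (stated 57).

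The planning figures are not in dispute.

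**2. Case 1: missing target, unequivocal non-target progression, no new lesion.**

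| Source | Overall assessment |
|---|---|
| 10.1.4 note | UN (its only exception, new disease, is absent) |
| 10.1.5 | PD by non-target progression |
| 10.1.6 table, Any / PD / Yes or No | PD |

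UN is one of the target categories in 10.1.4, so Any in the table includes it. The contradiction is explicit. It holds whether the note is triggered by one missing target lesion or only when all are missing.

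**3. Case 2: the measured target lesions alone pass the PD limit.** Illustrative sizes: smallest sum 20 + 20 + 10 = 50 mm. At the next scan two lesions measure 35 and 30 mm and the third is not measured.

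- A diameter cannot be negative, so the full sum is at least 35 + 30 = 65 mm.
- 65/50 − 1 = 30%, and 65 − 50 = 15 mm. Both limits (20%, 5 mm) are passed whatever the third lesion measures.

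The note gives UN if one missing target triggers it. The contrast with the second sentence, which requires data on all target lesions, supports that reading. Yet the assessment can be made, so the UN definition is not met. The conflict here is with that definition, not with a table row.

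**4. Size of a deferral.** Scans are every 8 weeks (every 8 to 16 weeks after one year on study, 5.1.10). 56/30.44 = 1.84 months, and 1.84/4.0 = 46% of the assumed Arm A median.

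**5. Effect on the primary test.** The share of progressions affected is not in the documents, so every share below is an assumption. Simulation: 20 v 40 patients, exponential PFS, accrual over 20 months, analysis at 40 months, progression seen at the next 8-week scan. Affected events move one scan later, or some are censored. With 4,000 to 5,000 runs the simulation error is about 0.004.

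| Assumed pattern | Result |
|---|---|
| None affected | power about 0.80; one-sided error 0.053 to 0.06 |
| 5% or 10% in both arms, delayed | power about 0.79 to 0.80; error 0.053 to 0.059 |
| 10% of Arm B only, delayed | error about 0.074 |
| 10% of Arm B only, half of them censored | error about 0.092 |

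If instead every affected event were lost to censoring, equally in both arms, the formula in step 1 gives:

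- 5% lost: 57 × 0.95 = 54.1 events, power 0.776.
- 10% lost: 57 × 0.90 = 51.3 events, power 0.757.

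Simulated error in those equal-loss cases stays at about 0.06.

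**The case against.** **Rarity.** Case 1 needs a missing target, unequivocal non-target progression (which the table footnote treats as exceptional) and no new lesion, all on one scan. That stands as a limit on frequency, but it does not remove the contradiction.

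**Case 2 is open to interpretation.** A reader may say that data which already prove progression are not insufficient, and so call target PD. The UN definition allows this and the mandatory note does not. Case 2 is therefore the weaker of the two.

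**Central review.** Real-time confirmation applies in either arm, and patients who stop for other reasons are reviewed later to adjudicate PFS. This makes a gross imbalance between arms less likely. It does not resolve the conflict, because the reviewers apply the same text.

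**Stronger readings that the documents do not support:**

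- *That these progressions are lost as PFS events.* Follow-up continues under Study Calendar D, and a later scan or death can still be recorded. The loss occurs only if other therapy, withdrawal or the end of follow-up comes first.
- *That every affected event is delayed by at least 8 weeks.* Imaging has a window of one week either way, an earlier repeat scan is not forbidden, and death is itself an event.
- *That the note's second sentence ignores new lesions.* It says "the overall response for that time point will be assigned based on the sum LD of all target lesions", but the PD definition in the same section and the table row Any / Any / Yes already make a new lesion PD.
- *That the false-positive rate is inflated.* This needs an imbalance between arms that nothing in the documents shows.

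**Conclusion.** The concern holds as an inconsistency in the rules that define the primary endpoint. It is explicit for Case 1. For Case 2 it depends on a literal reading of the note. Under the note, progression is not recorded at the affected scan. It is typically deferred by about 8 weeks (8 to 16 after one year), or replaced by censoring if other therapy starts first.

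The effect on the trial's conclusion is probably small. With equal application in both arms and deferral only, the test is essentially unaffected. Even with all affected events censored at an assumed 10% in both arms, power is 0.757 against 0.794. The rise in one-sided error from about 0.06 to between 0.074 and 0.092 rests wholly on the assumption that 10% of Arm B progressions, and none in Arm A, are affected. The stated 57 events and 80% power stand. The correction is still worth making, because it concerns an event definition and costs almost nothing.

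**What to change.** Replace the first sentence of the note in Section 10.1.4 with wording to this effect:

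> If any target lesion is not measured, the overall assessment is UN unless (a) there is a new lesion, (b) non-target disease has unequivocally progressed per Section 10.1.5, or (c) the measured target lesions alone sum to at least 20% and at least 5 mm above the smallest total sum on study. In (a) to (c) the assessment is PD, dated to that scan.

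Item (c) is a lower bound derived from the protocol's own limits, so it sets no new threshold. The second sentence of the note needs no change. The cost is one sentence, with no extra scans, data or patients, and no change to the sample size.
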